8.1.2 Screening activities performed after a consent for screening has been signed

The following activities will be performed only after the subject has signed the consent this study: lab assessments, imaging, physical exam. Assessments performed at outside facilities or on another NIH protocol within the timeframes below may also be used to determine eligibility once a participant has signed the consent form.

8.2 Study Evaluation & Procedures

The following procedures and imaging assessments will occur according to Section 1.3 Schedule of Activities.

All participants must sign the informed Consent Form (ICF) prior to any study-related procedures. Screening must be completed within 180 days prior to admission to the NIH CC (See [Table A](#) for Schedule of Activities).

Screening Visit: The first screening visit will be conducted at the NIH CC to determine subject eligibility, document current metabolic status, and assess dietary calcium intake. Participants may complete the screening assessments as outpatients or be housed overnight at NIH CC. Participants who complete the screening visit midweek have the option to stay overnight at NIH CC during the intervening days prior to Day -1. Each subject's current treatment regimen will be assessed by NIH investigators in relation to presence/absence and control of hypocalcemia-related complaints and symptoms, and assessment of blood and urine analytes including blood and urine calcium and phosphate. NIH investigators may recommend adjustments to a subject's outpatient regimen during the screening period, in accordance with the accepted goals of achieving cCa in the low normal range, while minimizing hypercalciuria. Unscheduled outpatient laboratory assessments, if required, will be arranged through outpatient laboratories with results transmitted to and reviewed by the investigators as standard of care. Participants who complete the screening process and meet inclusion/exclusion criteria, may be scheduled for admission for the treatment period of the protocol.

Procedures/evaluations planned as part of the screening visit include:

- History and Physical examination
- Height and Weight
- Vital Signs
- Nutritionist Assessment
- Blood laboratory assessment
- Electrocardiogram (ECG)
- 24-hour urine collection (may be performed after the visit if more convenient for the patient)

- Renal Ultrasound

After completing screening assessments, any AE/SAE reported by a subject, whether or not study drug has been administered, will be recorded by the investigators. Any AE/SAE prior to dosing will be categorized as “Baseline” and any AE/SAE after dosing will be categorized as “treatment-emergent.”

Treatment Period:

Day -2 or Day -1 (Admission): Participants will be admitted to the NIH CC either the day prior to dosing or two days prior to dosing based on subject convenience. All participants will be instructed to stop taking calcitriol and home calcium dosage, with last doses on Day -2. Participants on magnesium or potassium citrate will be instructed to stop these supplements, with last doses on Day -3. Calcium supplementation with calcium carbonate(500 mg elemental calcium) three times a day will start on Day -1. Baseline 24-hour urine will be opened the morning of Day -1, and fasting laboratory assessment will be obtained. Attempts will be made to collect fasting calcium levels prior to the morning calcium dosage, however, calcium will be given to participants if clinically indicated (for example, in the setting of hypocalcemia).

Days 1 to 5: Encaleret 162 mg BID will be taken orally by the patient. Detailed summary of planned calcium and calcitriol therapy is presented in Figure 2 and a dosing algorithm is presented in Table D. Frequent blood and urine sampling for 24-hours will be performed for safety and outcome measures (see [Table A and Table B](#)). Encaleret will be administered in the morning and evening with water approximately 12 hours between each dose. The last dose of study medication will occur on the evening of Day 5. Daily ECG will be performed for monitoring of QT interval.

Day 6 (Discharge): After the blood sampling is collected on the morning of Day 6 and the 24-hour urine is closed, all participants will resume their prior conventional treatment regimen. During Day 6, cCa levels will be monitored until the patient is discharged. This admission can be extended if additional monitoring or treatment (e.g., to stabilize calcium) is needed prior to discharge.

Follow-up:

Outpatient testing done on day 8-12 (Less than 7 days after expected discharge from the NIH clinical center) will be collected either at the NIH CC or local laboratory. Blood samples collected will be evaluated for blood creatinine, albumin, calcium, magnesium, phosphate, and PTH. A telephone contact to the patient will be conducted once calcium results are available to be reviewed with investigative team. Additional outpatient testing to follow up safety issues will be performed as needed.

An additional two telephone contacts will be performed at 30-days (\pm 7 days) and 90-days (\pm 7 days) after the last encaleret dose for screening of AEs and pregnancies, respectively.

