1 PROTOCOL SUMMARY

1.1 Synopsis

- Title:** Phase 2 study of the PTH-independent Effects of Encaleret on Mineral Homeostasis in subjects with post-surgical hypoparathyroidism (PSH)
- Study Description:** This will be a single-site, proof-of-principle, open-label study to explore the PTH-independent effects of encaleret on calcium homeostasis in participants with low or undetectable PTH levels as a result of neck surgery (PSH).
- Objectives:** *Primary Objective:*
- Evaluate the PTH-independent effects of encaleret on renal calcium handling in participants with PSH.
- Secondary Objectives:*
- Evaluate the ability of encaleret to normalize blood calcium while maintaining a normal urinary calcium in participants with PSH.
- Tertiary/Exploratory Objectives:*
- Evaluate the ability of encaleret to increase serum iPTH levels in participants with PSH.
 - Evaluate the effect of encaleret on 1-alpha hydroxylase action by measuring 1,25-(OH)₂ Vitamin D levels.
 - Explore the dynamic effect of encaleret on blood and urinary calcium, iPTH, cAMP, 1,25-(OH)₂ Vitamin D, and urinary citrate.
 - Evaluate the effect of encaleret on bone turnover in participants with PSH.
 - Evaluate the effect of encaleret on phosphate, magnesium, and FGF23 levels.
 - Explore the effects of encaleret on 24-hour urine markers that impact stone formation
 - Examine the PK of encaleret in participants with PSH and explore PK-PD interactions.
 - Explore the effect of encaleret on bone and mineral homeostasis in the following sub-groups, *as defined in Section 9.3:*
 - Permanent hypoparathyroidism (Cohort 1)
 - Recent hypoparathyroidism (Cohort 2)
 - “PTH-Clamp” cohort
 - “Aparathyroid” cohort
 - Hyperthyroid cohort
 - Normothyroid cohort
 - Thyroid cancer cohort

2

Primary Endpoint:

- Percent change in Fractional Excretion of Calcium (FECa) from baseline (Day -1) to the final day of treatment (Day 6 or the last measurement while on encaleret). FECa calculated using fasting blood levels and spot urine collection.

Secondary Endpoints:

- Proportion of participants who achieve a concomitant normal or elevated fasting blood calcium (albumin-corrected calcium >8.5 mg/dL) and a normal 24-hour urinary calcium level (<250 mg/24 hours for women, <300 mg/24 hours for men) on encaleret at any point between day 1 and day 5.

Tertiary/Exploratory Endpoints:

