2 INTRODUCTION

2.1 Study Rationale

This study will explore the PTH-independent effects of encaleret on calcium homeostasis in patients with low or undetectable PTH levels as a result of neck surgery (post-surgical hypoparathyroidism; PSH).

Hypoparathyroidism is characterized by an inappropriately low level of PTH which results in hypocalcemia. Inadequate PTH-secretion results in lower levels of endogenous 1,25-(OH)₂ Vitamin D (decreasing calcium absorption from the gut), lower levels of calcium reabsorption in the kidney (leading to hypercalciuria), and decreased PTH-mediated bone resorption (decreasing calcium release from the bone).

Conventional therapy with oral calcium and calcitriol, often causes hypercalciuria, which is associated with long-term morbidity including nephrolithiasis, nephrocalcinosis and chronic kidney disease (Khan et al 2018, Li et al 2018). Managing patients with hypoparathyroidism is a challenging balance between increasing blood calcium while minimizing hypercalciuria (Gafni and Collins, 2019).

To avert symptoms of hypocalcemia, patients with PSH usually require a blood calcium in the normal range. This often results in hypercalciuria and renal calcification, which in some cases leads to loss of renal function, including the need for dialysis and transplantation. As such, there is a significant unmet need in treating patients with PSH.

Encaleret is a negative allosteric modulator of the calcium-sensing receptor (CaSR), also known as a calcilytic, which decreases the sensitivity of the CaSR to calcium, resulting in decreased renal calcium excretion, and in patients with intact parathyroid glands, increased PTH secretion. Pre-clinical studies have showed that calcilytics shift the IC₅₀ of the calcium-PTH curve to the right (See IB Section 4.2.3 In Vivo Studies). In cellular and animal models of both post-surgical and genetic forms of hypoparathyroidism due to CaSR gain-of-function variants, calcilytics have been shown to shift the CaSR ‘set-point’ so as to increase renal reabsorption and PTH secretion (in animals with intact parathyroid glands), resulting in increased blood calcium (Loupy et al, 2012; Dong et al, 2015; Hannan et al, 2015).

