5 STUDY POPULATION

5.1 Inclusion Criteria

Participants must meet the following criteria for inclusion during screening:

1. Be able to understand and sign a written informed consent form, which must be obtained prior to initiation of study procedures.

2. Age \geq 18 years
3. Postmenopausal women are allowed to participate in this study:
 - a. Women are considered postmenopausal and not of childbearing potential if they have had 12 months of natural (spontaneous) amenorrhea with an appropriate clinical profile (e.g., age appropriate, history of vasomotor symptoms) or have had surgical bilateral oophorectomy (with or without hysterectomy) or tubal ligation at least 6 weeks prior to start of the study. In the case of oophorectomy alone, only when the reproductive status of the woman has been confirmed by follow up hormone level assessment, shall she be considered not of childbearing potential.
4. Body mass index (BMI) \geq 18.5 to $<$ 39 kg/m²
5. Have a diagnosis of PSH, either permanent PSH (Cohort 1, surgery \geq 12 months ago) or recent PSH (Cohort 2, surgery $<$ 12 months ago).
6. Participants must have achieved an albumin-corrected blood calcium level of 7.8-10.2 mg/dL on conventional therapy without significant symptoms of hypocalcemia or hypercalcemia.
7. Participants being treated with thiazide diuretics may be enrolled if they are willing and able to discontinue thiazides for at least 5 half-lives prior to initiation of encaleret and remain off during the study treatment period. (5 half-lives of hydrochlorothiazide = 75 hours; chlorothiazide = 10 hours; chlorthalidone = 12.5 days). If the thiazide is being used as an antihypertensive, as opposed to use as a urine calcium-lowering drug, alternative therapy will be offered.
8. Participants being treated with strong CYP3A4 inhibitors (including clarithromycin, telithromycin, nefazodone, itraconazole, ketoconazole, atazanavir, darunavir, indinavir, lopinavir, nelfinavir, ritonavir, saquinavir, tipranavir) may be enrolled if they are willing and able to discontinue these medications for at least 5 half-lives prior to initiation of encaleret and remain off during the study treatment period.
9. Participants being treated with magnesium or potassium citrate supplements should discontinue such treatment starting on Day -2.

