6.1.2 Dosing and Administration

On Day -1/-2, participants who met eligibility criteria at the screening visit will be admitted to the NIH CC. Participants will not take their magnesium and potassium citrate starting on the morning of Day -2. Participants will not take their standard-of-care calcium or calcitriol starting on the morning of Day -1, and will instead start a personalized calcium supplementation, determined by investigators from their baseline calcium requirements and levels. They will start on a dietary daily calcium intake of approximately 1000 mg per day, which may be adjusted if needed.

Encaleret 162 mg twice a day will be administered to participants on Day 1 to 5. Additional calcium and/or calcitriol will be administered per algorithm (Table D) if required.

Calcium and calcitriol supplementation will be adjusted following the algorithm delineated in Table D with the primary goal of safety. Mild to moderate symptomatic hypocalcemia at any calcium level, cCa < 7 mg/dL, or borderline QT prolongation, would cause investigators to give oral calcium and/or calcitriol. Doses will be determined at the discretion of experienced investigator's understanding of the patient's prior supplement requirements and severity of hypocalcemia. IV calcium may be used for participants with severe hypocalcemic symptoms or QTcF > 500 ms. If a patient develops mild hypercalcemia, then calcium and calcitriol will be held until cCa is less than 9 mg/dL. If cCa has not trended down by 12 hours (or earlier per investigator discretion), encaleret will be stopped. If cCa is > 12 mg/dL, encaleret will be discontinued and calcium and calcitriol will be held until cCa is < 9 mg/dL, when home regimen is restarted.

On Day 3, investigators will add calcitriol supplementation if the albumin-corrected calcium remains < 8.5 mg/dL. The calcitriol dose will be determined by investigators, taking into account the current calcium level and the subject's baseline requirements.

The last dose of encaleret will be given on the night of Day 5. The patient will then resume calcium and calcitriol and be discharged home. If the patient is hypercalcaemic or hypocalcemic, their baseline calcium and calcitriol may be adjusted at discharge. If needed, they may remain at the NIH clinical center until their labs have stabilized to a safe level.

Table D: Titration algorithm:

		Encaleret Titration	Calcium supplementation titration*	Calcitriol titration*	Additional interventions/ monitoring

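### The Day -1 FECa baseline leaves any effect of changing background therapy inside the encaleret estimate; a Day 1 pre-dose FECa is already collectable and should be a pre-specified sensitivity baseline

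*Combined protocol and SAP*

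**What the plan says.** Section 1.1 defines the primary endpoint as "Percent change in Fractional Excretion of Calcium (FECa) from baseline (Day -1) to the final day of treatment", using fasting blood and spot urine; Section 3 repeats it. Section 8.2 fixes when home treatment ends: "All participants will be instructed to stop taking calcitriol and home calcium dosage, with last doses on Day -2". It also fixes the baseline sample: "Baseline 24-hour urine will be opened the morning of Day -1, and fasting laboratory assessment will be obtained".

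The background regimen then changes. Under Section 6.1.2, home calcium and calcitriol are left off "starting on the morning of Day -1, and will instead start a personalized calcium supplementation". Section 8.2 describes the replacement differently: "Calcium supplementation with calcium carbonate(500 mg elemental calcium) three times a day will start on Day -1". Calcitriol may return from Day 3 if corrected calcium stays below 8.5 mg/dL, or earlier as rescue (Section 6.1.2, Table D). Section 8.3.9 acknowledges that maintenance medication is reduced or suspended.

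The trial is open-label with no control arm (Sections 4.1 and 6.3). Section 9.4.2 plans a one-sample t-test on the percent change, or a Wilcoxon signed-rank test if normality fails.

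A later pre-dose FECa can be computed. Table B has a spot urine with calcium and creatinine at Day 1 Time 0, Table C has mineral labs with calcium and creatinine at -30 and -15 minutes on Day 1, and Table A marks Day 1 as fasting. No FECa analysis names it as baseline. The only other named FECa baseline is the Screening visit, which is also on conventional therapy. For 1,25-(OH)₂ vitamin D, by contrast, the plan uses a Day 1 pre-dose baseline and only on-treatment values taken before calcitriol.

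Thiazide users must "discontinue thiazides for at least 5 half-lives prior to initiation of encaleret". That washout is tied to the first dose, not to Day -1.

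**The concern.** In a single-arm before-and-after comparison, the change from baseline contains everything that altered between the two samples. Here two things alter: encaleret is started, and home calcitriol and calcium are stopped and partly replaced. Section 2.1 gives a reason to think the second could matter: "Conventional therapy with oral calcium and calcitriol, often causes hypercalciuria". If leaving that therapy lowers FECa, part of the measured fall is not encaleret.

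The stated aim is to isolate a PTH-independent renal effect, so the size of the effect matters as well as its sign. The same measured change feeds the threshold in Section 6.1.2, under which a fasting FECa fall above 40% counts as the primary endpoint achieved and contributes to eligibility for discretionary early discontinuation. Nothing in Section 9.4 measures the background component or adjusts for it.

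**Working it through.** **1. Reproduce the plan's figures.** Inputs from Section 9.2: SD 20 (from 6 ADH1 subjects, mean change -66%), two-sided alpha 0.05, paired t-test. Power comes from the noncentral t distribution with n - 1 degrees of freedom and noncentrality δ√n/SD. The changes detectable with 80% power are 15.56% (n=15), 19.92% (n=10) and 33.64% (n=5). Rounded up, these are the stated 16%, 20% and 34%.

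**2. Timing.** From the morning of Day -1 to the morning of Day 6 is six days (there is no Day 0). The first is off drug and the next five are on drug. A Day 1 pre-dose baseline therefore removes one of the six days.

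**3. Illustration: encaleret has no effect.** Let w be the mean fall in FECa due to background change alone. No document gives w, so the values are assumptions. The chance of a significant result, from the formula in step 1 with δ = w and SD 20, is:

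| w | n=15 | n=10 |
|---|---|---|
| 0% | 5% | 5% |
| 5% | 15% | 11% |
| 10% | 44% | 29% |
| 16% | 82% | 62% |
| 20% | 95% | 80% |

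This is the plan's own power curve read at assumed background falls. It also borrows the SD of an on-drug response. The 95% confidence interval for an SD of 20 from 6 subjects is 12.5 to 49.1. At w = 10% and n = 15, the 44% becomes 82% at SD 12.5, 23% at SD 30 and 11% at SD 49.

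**4. Illustration: encaleret has a large effect.** If effects multiply, a total fall T leaves a drug effect e = 1 - (1 - T)/(1 - w).
- T = 66%: w = 10% gives 1 - 0.34/0.90 = 62.2%; w = 20% gives 57.5%; w = 30% gives 51.4%; w = 50% gives 32.0%. With n = 15 and SD 20, power stays above 99% up to w = 50%. It is 77% at w = 60%, where e = 15.0%.
- T = 40% (the achieved threshold): w = 10% gives 1 - 0.60/0.90 = 33.3%; w = 20% gives 25.0%; w = 30% gives 14.3%.

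**5. Thiazide.** Section 5.1 gives 75 h as five half-lives of hydrochlorothiazide, so one half-life is 15 h. At the minimum washout, a Day -1 sample 24 h before the first dose falls at (75 - 24)/15 = 3.4 half-lives. The residual is 2^-3.4 = 9.5%, against 2^-5 = 3.1% at the first dose. For chlorothiazide the stated minimum is 10 h, so a compliant participant could still be taking it at the Day -1 sample. Section 5.1 describes thiazide as lowering urine calcium. Residual drug would therefore lower the baseline FECa and shrink the apparent fall, a bias against encaleret.

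**6. Precision of the off-drug change.** If its SD were also 20 (assumption), the 95% interval at n = 15 has half-width 2.145 × 20/√15 = 11.1 percentage points.

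**The case against.** The strongest reply is that no document shows FECa falling when conventional therapy is withdrawn. Section 2.1 speaks of hypercalciuria, not FECa, and also attributes it to PTH deficiency, which withdrawal does not change. Section 3 describes FECa as relating urinary to blood calcium, so a lower urinary calcium need not mean a lower FECa. Home calcium is replaced rather than simply removed, and calcitriol may be back before Day 6, so the net change may be small, reversed or different between participants. All of this stands: the direction is an inference and the size is unknown. None of it supplies a control for the change.

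A second reply is that an effect near 66% would swamp any plausible drift. For the sign of the effect that is fair, as step 4 shows. But the 66% comes from ADH1, where Section 2.1 attributes the net effect to renal CaSR inactivation together with increased PTH signalling. It cannot simply be carried over, although Section 9.2 suggests that PSH kidneys may respond more.

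Third, replacing the primary baseline now is debatable. Section 2.3.1 already reports PTH findings from the first 6 PSH participants given encaleret, so a switch could look data-driven, and Day 1 removes only one day of drift. This also stands, and is why a sensitivity analysis is the better remedy.

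Finally, Section 9.1 defines FECa from 24-hour urine and 4-hour post-prandial blood. On that definition, the Day -1 collection already covers the first day off home therapy. The other endpoint sections use fasting values, so this does not settle the point.

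**Conclusion.** The point holds in a limited form. The Day -1 baseline is on, or one night after, conventional therapy; the trial has no control for the change in regimen; and a later pre-dose FECa is scheduled but unused. Any FECa change from altering background therapy is therefore attributed to encaleret.

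Its size cannot be taken from the documents. The 44%, 82% and 95% are conditional on assumed falls of 10%, 16% and 20%, SD 20 and n = 15. If the total fall is near 66%, the conclusion that FECa falls is safe over a wide range of w. What remains exposed is the effect size and the reading of the 40% threshold.

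A reader might infer more. One inference is that withdrawal will produce a positive trial without any drug effect, which the documents do not support because they neither show nor size such a fall. Another is that incomplete thiazide washout adds to a false positive, whereas on the protocol's own description it works the other way. A third is that Day -1 must be abandoned as the primary baseline, which the one-day gain does not justify.

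**What to change.** In Section 9.4.2:

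- Pre-specify a key sensitivity analysis of the primary endpoint with the Day 1 Time 0 pre-dose fasting FECa as baseline (Table B spot urine; Table C bloods at -30 and -15 minutes). This baseline also matches the anchor of the thiazide washout.
- Report the off-drug percent change from Day -1 to Day 1 with its 95% confidence interval beside the primary result. Given the width in step 6, do not read a non-significant change as no change.
- Report the primary result by calcitriol use (yes or no) before the final measurement. Label this descriptive, since calcitriol use depends on the calcium response on treatment.
- State that the whole Day -1 to Day 6 change will not be attributed to encaleret if the off-drug change is material.

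Do not plan a comparison of Day 1 to Day 2 with Day -1 to Day 1 unless a Day 2 fasting spot urine is added. Table B lists spot urine for calcium and creatinine only on Day -1 and at Day 1 Time 0.

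Separately, the statements of the Day -1 calcium regimen must be reconciled: Section 8.2 gives a fixed amount, while Section 6.1.2 and Table A make it individualised.

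The cost is wording; the baseline specimens are already scheduled. The downsides are that the reported reduction may be smaller, and that one day removes only part of any drift.
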